6 PARTICIPANT DISCONTINUATION/WITHDRAWAL

6.1 Participant Discontinuation/Withdrawal from the Study

Participants are free to withdraw from participation in the study at any time upon request. The reason for participant discontinuation or withdrawal from the study will be recorded on the final form. Subjects who sign the informed consent form and are randomized but do not receive the study intervention may not be replaced and will be included in the intent to treat analysis. Subjects who sign the informed consent form, and are randomized and receive the study intervention, and subsequently withdraw, or are withdrawn or discontinued from the study, will not be replaced and will be included in the primary analysis.

7 STUDY ASSESSMENTS AND PROCEDURES

7.1 Assessments and procedures

7.1.1 PROCEDURES

- Visual acuity (best-spectacle correction using Snellen)
- Clinical eye exam (including slit lamp examination to examine cornea, evaluate for keratic precipitates and their morphology and location, to assess for anterior chamber cell and flare)
- Intraocular pressure assessment
- Anterior chamber paracentesis: Trial I-Exam 0 (pre-study visit) and Exam 2 (day 7), and Trial II- during recurrence
- Endothelial cell morphology and density using specular microscopy or confocal microscopy: Trial I- Exam 1 and Trial II- Exam 7
- Laboratory screening/monitoring orders (complete blood count, CBC, and complete metabolic panel, CMP): Trial I-Exam 0,2, and 3 and Trial II- Exam 2-7

7.1.2 SPECIMENS

The following specimens will be collected

- *Anterior chamber aqueous fluid for CMV quantitative PCR: Trial I- at Exam 0 and Exam 2, Trial II- during recurrence*
 - Aqueous humor from Exam 0 will be divided into two parts, some of fluid will be used for in-house directed PCR for HSV, VZV, and CMV. The results will determine study eligibility. 50 microliters of fluid will be preserved in the event the patient is CMV positive, and amenable to participating in the trial, ultimately to be used for quantitative CMV PCR to be conducted at Proctor Foundation/UCSF.
 - Aqueous humor from Exam 2 in trial I and during recurrence in trial II designated for CMV quantitative PCR and RNA sequencing will be immediately labeled and frozen on site. Once all enrolled participants at the site have completed the study, their aqueous samples will be packaged together with sufficient dry ice and shipped to UCSF for testing.
- The following specimens will be collected for laboratory measurements *after Exam #0 and prior to enrollment and randomization (Day #1 of clinical trial)*

- Blood for complete blood count (CBC with differential)
 - Blood for serum chemistry panel (complete metabolic panel)
 - Blood or urine pregnancy test (all female participants of child-bearing age)
 - Blood for HIV testing (unless HIV status is known)
 - Blood for complete blood count (CBC with differential) and chemistry (complete metabolic panel): (Trial I; Exam 2 and 3, Trial II Exam 2-7)

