2b: We hypothesize that aqueous obtained at the time of a recurrence of inflammation will demonstrate a detectable viral load and will correlate with level of inflammation.

Specific Aim 3 (samples from Trials I and II): To characterize host transcriptional signatures and viral genomic features in CMV anterior uveitis using RNA sequencing of aqueous samples.

3a: We hypothesize participants completing both trials who exhibit recurrent inflammation after antiviral suppression (Trial II) will have a higher prevalence of CMV mutations associated with antiviral resistance compared to baseline samples (Trial I).

3b: We hypothesize that (i) host transcriptional profiles will distinguish CMV anterior uveitis from anterior uveitis cases negative for CMV and unable to enter Trial I, (ii) we will identify non-CMV pathogens in cases unable to enter Trial I, and (iii) we will identify unique signatures associated with recurrent inflammation in Trial II participants.

Study Population:

We plan to enroll 117 participants (39 participants per arm) across all sites.

Description of

Sites/Facilities

Enrolling

Participants:

Participants will be enrolled at 6 sites centered in the United States, Thailand and Taiwan. In Thailand, participants will be enrolled at Chulalongkorn University in Bangkok, Thailand, Khon Kaen University in Khon Kaen, Thailand and Chiang Mai University in Chiang Mai, Thailand. In Taiwan, participants will be enrolled at

Chang Gung Memorial Hospital. In the United States, participants will be enrolled at the Francis I. Proctor Foundation/UCSF and the University of California, Los Angeles. UCSF will serve as the clinical and data coordinating center.

Outcomes:

Trial I: Primary Endpoint: Viral load after 7 days of treatment

Secondary Endpoints:

- Clinical quiescence

Trial II: Primary Endpoint: Recurrence of inflammation over 12 months

Secondary Endpoints:

- Prevalence of mutations conferring antiviral resistance

Schema

Trial I

Pre-study visit (Exam 0)

Clinical eye examination reveals active anterior uveitis ($\geq 1+$ AC cell) and suggests a viral aetiology

[figure not shown]
- **Anterior chamber paracentesis** is performed to establish a viral aetiology
 - Half of fluid will be used for in- house directed PCR for HSV, VZV and CMV
 - At least 50 μ L of fluid will be preserved and used for quantitative CMV PCR to be conducted at a single US laboratory in eligible participants

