4 STUDY DESIGN

4.1 Overall Design

The Systemic and topical antiviral control of cytomegalovirus anterior uveitis: treatment outcomes (STACCATO) study will enroll participants with PCR-proven CMV anterior uveitis into a sequential double-masked randomized clinical trial in the US and Asia. In Trial I, participants will be randomized to one of the three treatment groups:

Group 1: Valganciclovir tablets 900 mg PO BID (4 tablets daily) and Placebo drops 1 drop 6 times daily

Group 2: Topical ganciclovir 2% 1 drops 6 times daily and Placebo tablets 2 tablets PO BID (4 tablets daily)

Group 3: Placebo tablets 2 tablets PO BID (4 tablets daily) and Placebo drops 1 drop 6 times daily

After participants achieve control of their inflammation, they will enter Trial II at which point they will be re-randomized to one of the three arms in Trial I at a prophylactic dosing. Additionally, patients with known CMV anterior uveitis, but who are inactive, may enter Trial II directly. Recurrences of inflammation in Trial II will be assessed for presence of detectable viral load. Those who agree to participate will be randomized at baseline and after achieving clinical quiescence, get re-randomized to one of the three treatment groups:

Group 1: Valganciclovir tablets 450 mg PO BID (2 tablets daily) and Placebo drops 1 drop BID

Group 2: Topical ganciclovir 2% 1 drop BID and Placebo tablets 1 tablet PO BID (2 tablets daily)

Group 3: Placebo tablets 1 tablet PO BID (2 tablets daily) and Placebo drops 1 drop BID

All study ophthalmologists and participants will remain masked to treatment assignment after enrollment. Due to the treatment design, all participants will receive both pills and eye drops. An interim analysis will be performed for both trials once primary outcome data is available for one third of the patients.

4.1.1 . STUDY MASKING PROCEDURES (EXAM #2 AND 3)

- The patient comes for the study visit and meets with the study coordinator before seeing their study doctor. This will facilitate masking of ophthalmologists and participants. All outcome assessors including lab technicians for trial I and ophthalmologists for trial II will remain masked. To facilitate interim and safety analysis, a data team member may also be unmasked.
- The patient's medication bottles are immediately placed in a secure, black bag and left at the study coordinators desk for the remainder of the visit. Patient medication calendars should also be placed in the black bag.

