4.3 End of Study Definition

A participant is considered to have completed the study if he or she has completed all visits and procedures and exams of the study described in Assessments and Procedures **Section 7.1**.

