8.3 Statistical Analyses

1a. The Aim 1 primary outcome **viral load after 7 days of treatment** will use the results from quantitative PCR at 7 days of treatment or placebo therapy (day 7 of trial). All quantitative PCR viral loads will undergo log transformation, with units converting from IU/mL to log IU/mL.

1b. **Clinical inactivity of inflammation:** At each study visit patients will be clinically examined, and a study ophthalmologist will make a clinical determination as to whether the patient's inflammation is considered inactive (defined as $\leq 0.5+$ anterior chamber cell). The proportion of participants that achieve clinically inactive inflammation by day 7 and 21 will be compared by arm. Patients will also be administered a questionnaire querying when they felt symptomatic improvement in their condition. This analysis will be viewed as hypothesis generating and will be treated as supplementary and in addition to the main finding.

2a. **Recurrence of inflammation over 12 months:** After achieving clinical quiescence, participants will be offered enrollment into Trial II where they would be re-randomized to long-term suppressive treatment to study the effect on recurrence of inflammation (defined as $\geq 1+$ anterior chamber cell). Each participant will be assessed for recurrence at each visit. Alternatively, if participants experience symptoms of a flare up, they will be instructed to contact the local site clinical coordinator or study ophthalmologist for an examination within 3 days. If recurrence of inflammation occurs, aqueous chamber fluid will be collected (an anterior chamber paracentesis will be performed) from participant to quantify viral load.

3a. **Prevalence of mutations conferring antiviral resistance:** The analysis population will include individuals enrolled in both Trials I and II who are randomized to receive oral or topical antivirals in Trial II and experience a recurrent infection. Among patients that experience a

recurrent infection (anticipated n=34, see Sample Size section 3.3 in SAP), we will compare the proportion of infections with antiviral mutations upon recurrence with the proportion with antiviral mutations at baseline.

Interim Analysis

The interim analysis for each trial should be conducted after one-third and before one-half of the patients have been enrolled; ideally when there are 15 patients per arm.

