8.3.1 SAFETY ANALYSES

Interim reports for the DSMC will be prepared by the central Proctor site.

The Data and Safety Monitoring Committee will meet to review the interim efficacy data when primary outcome data is available on one third of the study subjects. The DSMC will make one of the following recommendations:

- Continue the study without modifications
- Continue the study with modifications
- Terminate enrollment or treatment in the study because of safety concerns
- Terminate enrollment or treatment in the trial because of futility

The DSMC will determine the database closure dates for each report in advance; archival copies of the (a) main database, and (b) study analysis file as they exist at the time of each report will be maintained. All reports will be sent using secure email to the members of the DSMC two weeks prior to each meeting.

The DSMC will make decisions with the benefit of pre-specified decision guidelines. These guidelines will be agreed upon at the initial meeting, and are expected to include (a) safety, (b) efficacy, (c) futility, (d) clinical importance, or (e) validity.

Efficacy. Unmasked interim analyses will be conducted to determine whether or not sufficient evidence has accumulated to justify stopping the trial because one treatment is clearly superior (and therefore should be extended to all future cases). The guidelines for efficacy will use group sequential boundaries for judging the statistical significance of the primary outcome measure. The Lan and DeMets²³ flexible alpha spending approach with a power function is suggested, with $\alpha^*(t^*) = \alpha (t^*)^\theta$, where $\theta = 3.561$ chosen so that the two-sided *P*-value to stop the trial for efficacy is 0.001.

Harm. Stopping for harm will be done at the judgment of the DSMC. Several endpoints will be examined, including adverse events, and especially abnormal lab results meeting the designated threshold of a serious adverse event.

All subjects who provide informed consent will be accounted for in this study. We will present the number lost to follow-up and the number of protocol deviations by arm. The proportion of

subjects reporting adverse events and serious adverse events will be reported by arm to the DSMC and will be compared using a Fisher's Exact Test.

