### 3.5. Statistical interim analyses and stopping guidance

The interim analysis for both efficacy and futility will be conducted after one-third (1/3) and before one-half (1/2) of the patients have reached their primary endpoint; ideally when there are 15 patients per arm. With three arms and two primary comparisons of interest there are several scenarios for each interim analysis (Tables 2 and 3). The pre-specified action taken under each scenario will be agreed upon at the trial's first DSMC meeting. Separate interim analyses will be conducted for Trial I and Trial II, but will proceed similarly.

The DSMC will make one of the following recommendations:

- Continue the study without modifications
- Continue the study with modifications
- Terminate enrollment or treatment in the study because of safety concerns
- Terminate enrollment or treatment in the trial because of futility

The DSMC will determine the database closure dates for each report in advance; archival copies of the (a) main database, and (b) study analysis file as they exist at the time of each report will be maintained. All reports will be sent using secure email to the members of the DSMC two weeks prior to each meeting.

Table 2. Treatment Arms

Arm 1: Oral valganciclovir	Arm 2: Ganciclovir 2% eyedrop	Arm 3: Placebo
A	B	C

Table 3. Possible Scenarios in Interim Analysis for Efficacy

Scenario	Trial I/II interim result	Trial I/II interim result	Action for Trial I	Action for Trial II
	A vs B	A vs C		
1	A ~ B	A ~ C	Continue all arms	Continue all arms
2	A ~ B	A < C	DSMC discussion 	DSMC discussion 
3	A ~ B	A > C	DSMC discussion 	DSMC discussion 
4	A < B	A ~ C	DSMC discussion 	DSMC discussion 
5	A < B	A < C	DSMC discussion 	DSMC discussion 
6	A < B	A > C	DSMC discussion 	DSMC discussion 
7	A > B	A ~ C	DSMC discussion 	DSMC discussion 

DSMC discussion will be triggered in such a scenario to discuss the continuation or cessation of arm(s). Pre-specified actions for each scenario will be agreed upon between the investigators and the members of the DSMC at the trial's first DSMC meeting.

The DSMC will make decisions with the benefit of pre-specified decision guidelines. These guidelines will be agreed upon at the initial meeting, and are expected to include (a) safety, (b) efficacy, and (c) futility.

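### The specimen rule holds day-7 samples at each site until the site has finished, so the Trial I viral-load interim cannot be done in its one-third to one-half window unless UCSF and already-closed sites supply most of the early participants

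*Protocol*

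**What the plan says.** **Where the outcome is measured.** The schema in the Protocol synopsis sends the preserved Exam 0 aliquot for "quantitative CMV PCR to be conducted at a single US laboratory in eligible participants". Protocol 7.1.2 names that laboratory as Proctor Foundation/UCSF and sends the Exam 2 (day 7) aqueous there for testing as well.

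**When samples leave the site.** Protocol 7.1.2 has Exam 2 and recurrence samples frozen on site, then: "Once all enrolled participants at the site have completed the study, their aqueous samples will be packaged together with sufficient dry ice and shipped". Protocol 4.3 says a participant is "considered to have completed the study if he or she has completed all visits and procedures and exams of the study" set out in Section 7.1. Section 7.1.1 covers both trials: "Anterior chamber paracentesis: Trial I-Exam 0 (pre-study visit) and Exam 2 (day 7), and Trial II- during recurrence".

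**When the interim is due.** Four passages bear on this:

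- Protocol 8.3: the interim "should be conducted after one-third and before one-half of the patients have been enrolled; ideally when there are 15 patients per arm".
- SAP 3.5: it "will be conducted after one-third (1/3) and before one-half (1/2) of the patients have reached their primary endpoint".
- Protocol 4.1: "An interim analysis will be performed for both trials once primary outcome data is available for one third of the patients".
- Protocol 8.3.1: the DSMC will "review the interim efficacy data when primary outcome data is available on one third of the study subjects".

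Neither document provides for an interim shipment, rolling assay, or local quantitative PCR of day-7 samples.

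**The concern.** The specimen rule and the interim rule cannot both be followed on an ordinary course of enrolment. A tube in a site freezer is not outcome data, and a site that is still enrolling or following participants has shipped nothing.

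At stake is the one pre-specified efficacy and futility look in Trial I. Either the DSMC sees it after the one-half limit, when fewer participants are left to benefit from stopping, or it sees results only from UCSF and any sites that have already closed. The futility guidance is framed around participants not yet enrolled, so it loses its use if results arrive only as sites finish.

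**Working it through.** **Inputs.** 117 participants, 39 per arm, at 6 sites including UCSF (Protocol synopsis). Evaluable target 35 per arm, 105 in all (SAP 3.3). Preferred interim size 15 per arm (Protocol 8.3, SAP 3.5). Trial I ends at day 21 and Trial II lasts 12 months (Protocol synopsis). Alpha 0.025 per comparison, spending exponent 3.561, interim threshold 0.0005 (SAP 3.5).

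**1. The plan's own threshold.** 0.025 × (1/3)^3.561 = 0.0005. This matches SAP 3.5, so the stated threshold belongs to a look at one-third of the information.

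**2. The window in participants.**

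| Base | One-third | Last count before one-half | Preferred size |
|---|---|---|---|
| 117 enrolled | 117/3 = 39 | 117/2 = 58.5, so 58 | 15 × 3 = 45 |
| 105 evaluable | 105/3 = 35 | 105/2 = 52.5, so 52 | 45 |

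**3. What can be assayed inside the window.** Only UCSF's samples, which need no shipment, and those from sites where everyone has finished. Among the first 58 participants with Exam 2 done, these must supply:

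- 39/58 = 67% to reach one-third of outcomes;
- 45/58 = 78% to reach 15 per arm.

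At that point 117 − 58 = 59 participants are still to come.

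**4. How likely that is.** The documents give no site shares, so UCSF's share is an assumption. With no other site closed, the results available at 58 participants are:

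| Assumed UCSF share | Results at 58 participants |
|---|---|
| 10% | 6 |
| One-sixth (equal sites) | 58/6 ≈ 10 |
| 50% | 29 |

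All are below 39. With equal sites of 117/6 = 19.5, reaching 39 takes every UCSF participant plus one fully finished site.

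**5. How long a sample is held.** Take the day-7 sample of a site's last Trial I participant.

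- If completion means Trial I only: at least 21 − 7 = 14 days.
- If that participant enters Trial II at day 21 to 35 and completes 12 months: 21 + 365 − 7 = 379 days to 35 + 365 − 7 = 393 days. The entry range is an assumption, with the two-week washout starting at day 7 or day 21. The documents set no latest entry date, so 393 is not an upper limit.

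Samples from earlier participants wait longer, because they wait for the last one. Accrual and site-closure dates are not given, so the actual delay to the interim cannot be computed.

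**The case against.** **The sentence may mean Trial I only, and participants enrolled to date.** On that reading a site could ship at an interim cut. But the same paragraph of 7.1.2 governs Trial II recurrence samples and has a site's samples sent together, which describes one shipment at the end. Reading it as Trial I alone does not help either, because a site still enrolling in Trial I has not finished. If a to-date reading was intended, the text needs to say so.

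**The definition in 4.3 cannot be the working trigger.** Taken literally, a site with one dropout would never ship. This is a fair criticism of the wording, but it makes the conflict worse, and the conflict does not depend on 4.3.

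**Details may sit in the manual of procedures.** That manual is not among the documents, and it cannot be assumed to override the Protocol.

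**The window is guidance and the spending function is flexible.** This stands as far as type I error goes: a shifted look can be accommodated. It does not supply the missing results.

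**Early stopping is unlikely anyway.** This largely stands. With the plan's inputs (difference 0.50, SD 0.66, 35 per arm), the expected final Z is 0.50/(0.66 × √(2/35)) = 3.17. At one-third, the chance of crossing the efficacy boundary is 1 − Φ(3.48 − 3.17 × √(1/3)), about 5% per comparison. It is about 8% at 45 of 117 and 20% at one-half. Under no effect, the chance that both comparisons fall below 20% conditional power is about 7%, 14% and 37% at the same looks, assuming a correlation of 0.5 between them. These figures limit the practical loss. They do not justify a plan that cannot produce the look it promises.

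**Single-batch testing protects assay comparability.** True, and it is the real cost of the fix.

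**Conclusion.** The concern holds. Followed as written, Protocol 7.1.2 defeats the Trial I interim set out in Protocol 4.1, 8.3 and 8.3.1 and SAP 3.5. The window is 39 to 58 of 117 participants, and it can be met only if UCSF and already-closed sites supply at least 67% of the first 58 (78% for 15 per arm). The documents neither exclude that nor suggest it.

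The conclusion rests on the shipping sentence as it stands and on UCSF being the only quantitative laboratory. It does not rest on the holding-time figures or on any assumed site share. Type I error, the Trial II interim (recurrence is graded clinically on site) and the safety review are unaffected. SAP 3.6 is not contradicted, because it gives only a minimum time before the final analysis. The passages should be reconciled before the interim falls due.

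**What to change.** Amend Protocol 7.1.2 as follows.

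- **Interim batch.** Trigger a shipment from every non-UCSF site by the trial-wide count of participants with Exam 2 done. Set it at or just after 39 and no later than about 45, so that shipping and assay finish before one-half. The room left is 58 − 39 = 19 participants, or 58 − 45 = 13. On a base of 105 it is 52 − 39 = 13, or 52 − 45 = 7.
- **Paired samples.** Send each participant's preserved Exam 0 aliquot with the Exam 2 sample and assay both in one run. The primary model in SAP 6.2 adjusts for baseline viral load, and 7.1.2 gives the Exam 0 aliquot no explicit shipping time.
- **Later batches.** Ship the remaining Trial I samples when Trial I ends at the site, and Trial II recurrence samples afterwards.
- **Aim 3.** Keep material so that baseline and recurrence samples can still be sequenced together. Check that the volume allows it, since the synopsis assures only 50 μL for the Exam 0 quantitative PCR.

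**Cost.** Up to two extra dry-ice shipments per non-UCSF site (5 × 2 = 10 at most) and at least one extra PCR run. Some batch variation remains. Pairing Exam 0 with Exam 2 in one run, and randomization in blocks within site, limit its effect on the arm comparison. No endpoint or sample size changes.
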